3.0 OBJECTIVES AND ENDPOINTS

Table 2 presents the primary, secondary immunological and safety objectives as well as exploratory objectives and corresponding endpoints.

Table 2 Study Objectives and Corresponding Endpoints

Objectives	Endpoints
Primary	

 The primary objective is to evaluate the safety and tolerability of the GBS-NN/NN2 vaccine for 4 weeks after each dose of vaccine. 	
 Safety and tolerability as determined by the occurrence of AEs consisting of local and systemic reactogenicity within 7 days after vaccination (Days 1 through 8 post each dose of the IMP) Unsolicited AEs, including AESIs, MAAEs and SAEs within 28 days after each vaccination AESIs, MAAEs, ARs/SARs leading to withdrawal from the study.
Secondary Immunological	

 To evaluate IgG antibody response to the GBS-NN/NN2 vaccine at Day 197 (principal immunological endpoint). To evaluate IgG antibody responses induced by the three vaccine doses, on a 0-, 1- and 6-month regimen, in older adult participants 4 weeks after each vaccination. To assess whether pre-existing antibody levels affect the vaccine-induced antibody response. To evaluate the immune response up to 6 months following the 3rd dose; to be reported in an addendum to the main CSR. 	
 Geometric mean antibody concentration in µg/mL for antibodies to the four individual Alps (Alp 1, Alp2/3, Rib and AlpC). Geometric mean fold increase in antibody concentration for antibodies to the four individual Alps (Alp 1, Alp2/3, Rib and AlpC). Seroconversion rate (proportion of participants with a 4-fold increase above baseline – pre dose concentration) at any time post vaccination. Proportion of participants achieving antibody concentrations for antibodies to the four individual Alps (Alp 1, Alp2/3, Rib and AlpC) above specific thresholds at Days 29, 57, 169, and 197 (these thresholds will be 1, 2, 4, and 8 µg/mL).
Secondary Safety	

 To evaluate the long-term safety profile of the GBS-NN/NN2 vaccine between Day 57 (28 days post second injection) to Day 168 and 6 months 	
 Proportion of participants with any SAE from between Day 57 (28 days post second injection) to Day 168 and 28 days after 3rd vaccination (Day 197) up to Day 365.

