8.3.4 Regulatory Reporting Requirements for SAEs

Prompt notification by the investigator to the Sponsor or designee of an SAE is essential so that legal obligations and ethical responsibilities toward the safety of participants and the safety of an IMP under clinical investigation are met.

The Sponsor has a legal responsibility to notify both the local regulatory authority and other regulatory agencies about the safety of an IMP under clinical investigation. The Sponsor will comply with country-specific regulatory requirements relating to safety reporting to the regulatory authority, EU Eudravigilance Database (as applicable), IRBs/IECs, and Investigators.

An investigator who receives an investigator safety report describing an SAE or other specific safety information (eg, summary or listing of SAEs) from the Sponsor will review and then file it along with the IB and will notify the IRB/IEC, if appropriate according to local requirements.

Investigator safety reports must be prepared for SUSARs according to local regulatory requirements and Sponsor policy and forwarded to Investigators as necessary.

8.3.5 **Solicited Adverse Events**

Local and systemic predefined solicited AEs for reactogenicity assessment will be collected by the participant in a solicited AE eDiary for 7 days following each study vaccination. The set of solicited AEs associated with reactogenicity are presented in Table 4.

Table 4 Reactogenicity Assessment: List of solicited adverse events

Local	Systemic
Pain at the site of injection	Fever (>100°F [>37.9°C]) ^a
Erythema/redness at the site of injection	Chills
Tenderness	Muscle pains
Induration/swelling at the site of injection	Fatigue
Itching	Headache
	Malaise
	Nausea
	Vomiting

^a Fever measured orally. Investigators who consider a temperature lower than this cutoff as a fever or a ‘fever’ reported by participants without documentation by a thermometer should record the event as ‘elevated body temperature’.

8.3.6 **Adverse Events of Special Interest and Medically Attended Adverse Events**

Adverse events will be monitored throughout the study to identify any event of interest that may indicate a trend or risk to participants. The following are considered adverse events of special interest (AESI):

- Development of autoimmune diseases
- GBS infections
- Symptomatic GBS urinary tract infections

A MAAE is an AE that leads to an unscheduled visit to a health care provider.

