9.4.1 Safety Analysis

The percentage of participants with at least one solicited AE (local and systemic), with at least one unsolicited AE, and with any AE during the 7-day or the 28-day follow-up period will be tabulated after each vaccination and overall. Similar tabulation will be done for Grade 3 events, any AESIs, any MAAEs, any AEs considered related to the vaccination and any Grade 3 AEs considered related to vaccination.

The percentage of participants reporting each individual solicited local and general AE during the 7-day follow-up period will be tabulated over the three doses.

The percentage of participants with unsolicited AEs, including AESIs, MAAEs and SAEs within 28 days after any doses will be tabulated by treatment and by Medical Dictionary for Regulatory Activities (MedDRA) preferred term. Similar tabulation will be done for Grade 3 unsolicited AEs and for Grade 3 and causally related unsolicited AEs and for unsolicited AEs causally related to vaccination.

The number of participants who experienced at least one SAE during the entire study period will be reported. The number and percentage of participants with AESIs, MAAEs, AEs/SAEs, and ARs/SARs leading to withdrawal from the study or discontinuation of the treatment will be tabulated.

The number and percentage of participants with any SAE, AESIs, MAAEs, ARs/SARs leading to withdrawal from the study between Day 57 (28 days post second injection) to Day 168 and from 28 days after 3rd vaccination up to Day 365 will also be summarised by treatment group.

All laboratory test results, and vital signs measurements will be summarised for each treatment group using descriptive statistics at each visit for observed and change from baseline values. The incidence of treatment-emergent abnormal laboratory values will also be summarised using descriptive statistics.

Further details will be provided in the SAP.

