3. STUDY ENDPOINTS

3.1. Primary Endpoints

- Safety and tolerability, as determined by the occurrence of adverse events (AEs) consisting of local and systemic reactogenicity, within 7 days after vaccination (Days 1 through 8 post each dose of investigational medicinal product (IMP))
- Unsolicited AEs, including AE of special interest (AESIs), medically attended AEs (MAAEs) and serious AEs (SAEs) within 28 days after each vaccination
- AESIs, MAAEs, adverse reactions (ARs)/serious adverse reactions (SARs) leading to withdrawal from study

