- Doses without diary completed will be excluded

The number and percentage of participants with unsolicited AEs within 28 days after any doses with its exact 95% CI will be tabulated by system organ class and preferred term for each treatment group. Similar tabulation will be done for

- severe (grade 3) unsolicited AEs
- unsolicited AEs causally related to vaccination
- severe and causally related unsolicited AEs
- unsolicited AEs of special interest (AESIs)
- unsolicited AEs requiring medical attendance (MAAEs)

The incidence of solicited adverse events (local and systemic) with severity will be plotted using horizontal bar charts. For the purpose of this plot, severity will follow the definitions according to the [FDA Guidance for Industry: Toxicity Grading Scale for Healthy Adult and Adolescent Volunteers Enrolled in Preventive Vaccine Clinical Trials \(September 2007\)](#). For example, the result collected in eCRF will correspond to following severity grades:

Injection Site Pain:

Awareness of injection site pain, but easily tolerated: Mild or Grade 1

Injection site pain is affecting normal activities: Moderate or Grade 2

Unable to do normal activities, health is affected, and needs medication or visit: Severe or Grade 3

Systemic Events (Chills, Muscle Pains, Fatigue, Headache, Malaise, Nausea, Vomiting):

Awareness but easily tolerated: Mild or Grade 1

Affecting normal activities: Moderate or Grade 2

Unable to do normal activities: Severe or Grade 3.

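### SAP 17.1 tabulates 28-day medically attended AEs only among unsolicited AEs and leaves out the any-MAAE table planned in protocol 9.4.1

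*SAP*

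**What the plan says.** **Definition.** Protocol 8.3.6: "A MAAE is an AE that leads to an unscheduled visit to a health care provider". The definition turns on the visit and does not limit the kind of AE.

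**Planned tables.** Protocol 9.4.1 contains two separate plans.
- The first paragraph covers participants with solicited AEs, unsolicited AEs and any AE over the 7-day or 28-day period, after each vaccination and overall. It continues: "Similar tabulation will be done for Grade 3 events, any AESIs, any MAAEs, any AEs considered related to the vaccination".
- The third paragraph is a preferred-term table by treatment: "The percentage of participants with unsolicited AEs, including AESIs, MAAEs and SAEs within 28 days after any doses will be tabulated".

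**Primary endpoint.** Protocol Table 2 lists "Unsolicited AEs, including AESIs, MAAEs and SAEs within 28 days after each vaccination". SAP 3.1 carries this over: "Unsolicited AEs, including AE of special interest (AESIs), medically attended AEs (MAAEs) and serious AEs (SAEs) within 28 days after each vaccination".

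**SAP tables.** SAP 17.1 tabulates solicited AEs by occurrence and severity, per dose and overall. It then tabulates 28-day unsolicited AEs by system organ class and preferred term, with subset tables that include "unsolicited AEs requiring medical attendance (MAAEs" and "unsolicited AEs of special interest (AESIs". Its text contains no table of any MAAE. SAP 17.1.1 names MAAEs twice more: among events leading to withdrawal or discontinuation, and in the late follow-up windows (Day 57 to 168, and from 28 days after the third dose to Day 365). SAP 4.3 states that the analyses are unchanged from the protocol.

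**The concern.** The primary objective is safety and tolerability in the four weeks after each dose, and medical attendance is one of the few markers of how much an event mattered to the participant. If the MAAE count admits only unsolicited events, a diary-recorded vaccine reaction that led to a doctor's visit appears in the solicited tables with its grade, but the visit is not tabulated.

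The solicited grades do not substitute for this. For injection site pain, SAP 17.1 describes the top grade as "Unable to do normal activities, health is affected, and needs medication or visit: Severe or Grade 3". That wording merges taking medication with seeking care. It also shows that a visit for a solicited reaction was foreseen.

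At stake is a stated counting rule that can undercount medically attended vaccine reactions. The protocol's broader tabulation has been dropped without being declared.

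**Working it through.** The plan states no MAAE rate or related figure, so there is nothing to reproduce. The check compares the texts and then illustrates the size.

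**Step 1. Which tables could count a medically attended solicited reaction?**

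| Table | Limited to unsolicited AEs? | Counts the event as an MAAE? |
|---|---|---|
| Protocol 9.4.1, paragraph 1, any MAAE | No | Yes, per dose and overall; absent from SAP 17.1 |
| SAP 17.1, 28-day MAAE | Yes | Not if the event is classed as solicited |
| SAP 17.1, solicited AEs | Solicited only | No; occurrence and grade only |
| SAP 17.1.1, withdrawal or discontinuation | No | Only if the event had that consequence |
| SAP 17.1.1, late windows | No | Not at nominal visit days (step 2) |

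**Step 2. Do the late windows help?** The eDiary covers the vaccination day and the next 6 days (protocol 8.2.4). With doses on Days 1, 29 and 169, the solicited periods are Days 1 to 7, 29 to 35 and 169 to 175. All lie outside Day 57 to 168 and outside the window that opens 28 days after dose 3. One exception follows from the visit window of Day 169 ± 7. A third dose on Day 162 gives a solicited period of Days 162 to 168, which would fall in the earlier window if it is applied by fixed study day. That overlap is incidental, and the table is not a 28-day count.

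**Step 3. Worked case.** Participant A records severe injection site swelling in the eDiary on Day 3 and sees a doctor on Day 4. Participant B has a rash, which is not a solicited term, and sees the same doctor. Both meet protocol 8.3.6. If A's event is kept as solicited, the SAP 17.1 MAAE table counts B and not A.

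**Step 4. Does the same apply to AESIs?** Protocol 8.3.6 lists autoimmune disease, GBS infection and symptomatic GBS urinary tract infection. None is a solicited term in protocol Table 4, so limiting AESIs to unsolicited events excludes none of them.

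**Step 5. Illustrative size.**
- Inputs: 24 vaccinated participants per healthy cohort and 12 per obese/diabetic cohort (protocol 9.2); Clopper-Pearson 95% limits (SAP 7.1).
- Assumption, not from the documents: one participant in the group has a medically attended solicited reaction, and nobody else has an MAAE.
- For x = 0, the upper limit is 1 − 0.025^(1/n).
- For x = 1, the lower limit is the 0.025 quantile of Beta(1, n) and the upper limit is the 0.975 quantile of Beta(2, n − 1).

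| n | Event omitted | Event counted | Change |
|---|---|---|---|
| 24 | 0/24 = 0% (0 to 14.2%) | 1/24 = 4.2% (0.1 to 21.1%) | 4.2 points |
| 12 | 0/12 = 0% (0 to 26.5%) | 1/12 = 8.3% (0.2 to 38.5%) | 8.3 points |

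These figures would hold for any one miscounted participant. They show the scale and do not predict how many such events will occur.

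**The case against.** **The SAP follows the protocol's own endpoint.** The primary endpoint, the third paragraph of 9.4.1 and the eDiary text in 8.2.4 all place MAAEs with unsolicited AEs, and SAP 17.1 implements that table. This stands: a reader might infer that the SAP simply contradicts the protocol, and the documents do not support that. However, 9.4.1 lists two tabulations, and implementing one does not account for the other. Dropping it is a change that SAP 4.3 should have declared.

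**The visit might be recorded as unsolicited anyway.** Protocol 10.3.1 defines an unsolicited AE by spontaneous reporting and asks participants to contact the site about medically attended events. A swelling entered in the eDiary and then reported by telephone because of a doctor's visit fits both descriptions. This stands in part. Exclusion from the table is not certain, but neither document gives a rule, so the count would depend on site practice.

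**The event is not lost.** A reader might infer that such a reaction is never counted. That goes too far. It stays visible by grade in the solicited tables, the visit may appear in listings, and SAP 17.1.1 counts it as an MAAE if it led to withdrawal or discontinuation. One could even read the qualifier in that sentence as attaching only to the adverse reactions, so that all MAAEs are tabulated there. The section's title points the other way, and the sentence specifies no 28-day or per-dose count.

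**Few events are likely.** Protocol 2.3.1 reports mild, self-limiting injection site pain and no significant or persistent reactions. This stands and limits the practical weight of the point.

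**The templates are not visible.** SAP 9 refers to output templates that may contain an any-MAAE row. That cannot be excluded, but the SAP text should still specify the table.

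**Conclusion.** The point holds in a limited form. SAP 17.1 omits the any-MAAE tabulation planned in the first paragraph of protocol 9.4.1. The narrower table it retains need not count a medically attended solicited reaction, and no change is declared.

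The conclusion rests on two assumptions: that such a reaction keeps its solicited classification, and that the templates contain no additional table.

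Any omission can only lower the reported MAAE rate. Because the placebo is saline, it is reasonable to expect solicited reactions mainly in the vaccine groups. A reader might go on to infer a material bias in favour of the vaccine. The documents do not support that: they give no MAAE rate, the reactions known so far are mild, and SAP 17 plans no statistical comparison of safety data. The size is unknown beyond the illustration of 4.2 or 8.3 points per omitted participant.

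Nor is there an AESI undercount to correct. The point concerns MAAEs only. It is worth settling because the correction is small and the count belongs to the trial's primary safety question.

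**What to change.** 1. Keep the unsolicited MAAE table in SAP 17.1, since it matches the primary endpoint and the third paragraph of protocol 9.4.1.
2. Add the table from the first paragraph of 9.4.1: number and percentage of participants with any MAAE, solicited or unsolicited, with exact 95% CI, by treatment group, after each vaccination and overall. Count each participant once per column, and footnote how many had an MAAE that was a solicited reaction.
3. State that a solicited reaction leading to an unscheduled health care visit is flagged as an MAAE on the AE page during the eDiary review that site staff already perform (protocol 6.6).
4. Leave the AESI table as it is.

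If the sponsor intends to report only unsolicited MAAEs, the alternative is to declare that restriction in SAP 4.3 and state how medically attended solicited reactions are classified.

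The cost is one more table, one sentence in the SAP and a short site instruction, with no new visit. The reported MAAE rate may be slightly higher.

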17.1.1. TEAEs Leading to Discontinuation of Study Medication or Withdrawal from Study

Treatment emergent adverse events (TEAEs) leading to permanent discontinuation of study medication will be identified by using the variable “Action taken with study treatment” = “Permanently withdrawn” from the AE page of eCRF and will be listed.

TEAEs leading to withdrawal from study will be identified by using the variable “Did the subject withdraw from study due to this event” = “Yes” from the AE page of eCRF and will be listed.

The number and percentage of participants with AESIs, MAAEs, AEs/SAEs, and ARs/SARs leading to withdrawal from the study or discontinuation of the treatment will be tabulated by SOC and PT.

The number and percentage of participants with any SAE, AESIs, MAAEs, ARs/SARs leading to withdrawal from the study between Day 57 (28 days post second injection) to Day 168 and from 28 days after third vaccination up to Day 365 will be summarised by treatment group and by SOC and PT.

Document: \\dccar2dnetvnasc01p-lan1.quintiles.net\cp_ops\BIOS\MinervaX\GBS-
NN_NN2\MVX0006\Biostatistics\Documentation\SAP

Author: [REDACTED] Version Number: 1.0

Version Date: 19APR2024

Template No.: CS_TP_BS016 Revision 7

Reference: CS_WI_BS005

Effective Date: 01Nov2021

Note: Adverse reactions (ARs) are defined as adverse events considered related to vaccination.

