3.3. Secondary Safety Endpoints

- Proportion of participants with any SAE from Day 57 (28 days post 2nd injection) to Day 168 and 28 days after 3rd vaccination (Day 197) up to Day 365
- Proportion of participants with MAAEs, AESIs, ARs/SARs requiring a medical consultation, and/or leading to withdrawal from study from 28 days after 3rd vaccination (Day 197) up to Day 365

Document: \\dccar2dnetvnasc01p-lan1.quintiles.net\cp_ops\BIOS\MinervaX\GBS-
NN_NN2\MVX0006\Biostatistics\Documentation\SAP

Author: [REDACTED] Version Number: 1.0

Version Date: 19APR2024

Template No.: CS_TP_BS016 Revision 7

Reference: CS_WI_BS005

Effective Date: 01Nov2021

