17.1.2. Serious Adverse Events

Participants who experienced at least 1 SAE within 28 days after any dose, from dose 1 until 28 days post last dose and during the entire study period will be listed.

The number and percentage of participants with any SAE and SARs between Day 57 (28 days post second injection) to Day 168 and from 28 days after third vaccination up to Day 365 will be summarised by treatment group and by SOC and PT.

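### The only long-term table of AESIs and MAAEs sits in the SAP's withdrawal section with a withdrawal qualifier, so non-serious events in participants who stay in the study may be listed but not tabulated by group

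*SAP*

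**What the plan says.** The SAP handles AESIs and MAAEs in three places.

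- **Section 17.1** asks for "The number and percentage of participants with unsolicited AEs within 28 days after any doses", with similar tables for AESIs and MAAEs. These inherit the 28-day limit.
- **Section 17.1.2** covers both long-term windows but only for serious events: "The number and percentage of participants with any SAE and SARs between Day 57" to Day 168, and from 28 days after dose 3 to Day 365. It has no withdrawal condition and does not name AESIs or MAAEs.
- **Section 17.1.1** is headed "TEAEs Leading to Discontinuation of Study Medication or Withdrawal from Study" and identifies study withdrawals by the eCRF item "Did the subject withdraw from study due to this event” = “Yes". It then specifies, for both long-term windows, a table of participants "with any SAE, AESIs, MAAEs, ARs/SARs leading to withdrawal from the study".

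The endpoint that the last table should serve is the second bullet of SAP 3.3: "Proportion of participants with MAAEs, AESIs, ARs/SARs requiring a medical consultation, and/or leading to withdrawal from study from 28 days after 3rd vaccination" up to Day 365.

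Protocol 9.4.1 contains the same sentence as 17.1.1, but as part of the general safety analysis. SAP 4.3 declares no changes from the protocol. Protocol 8.3.1 collects all MAAEs, AESIs and SAEs in the long-term periods, whether or not the participant withdraws.

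**The concern.** The long-term windows exist to detect late events. Protocol 8.3.6 names the development of autoimmune disease and GBS infection as AESIs. It defines a MAAE by an unscheduled visit to a health care provider, which need not lead to leaving the study. Under protocol 7.1, even a participant who permanently stops the vaccine stays in the study for safety evaluation. Withdrawal because of an event is therefore a narrow filter.

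A programmer who works from 17.1.1 finds a withdrawal heading, a withdrawal flag and a sentence that ends in a withdrawal qualifier, and could reasonably apply the filter to the whole list. A non-serious AESI or MAAE in a continuing participant would then appear in no by-group table, and the second endpoint of SAP 3.3 would go unreported as defined.

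**Working it through.** The plan states no figure on this point. The check is which event types are tabulated in which window, followed by a count of days and an illustration.

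**1. Coverage of the specified tables**

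| SAP section | Window | Events | Withdrawal condition |
|---|---|---|---|
| 17.1 | within 28 days of a dose | unsolicited AEs, including AESIs and MAAEs | none |
| 17.1.2 | Day 57-168; 28 days after dose 3 to Day 365 | SAEs, SARs | none |
| 17.1.1, disputed sentence | the same two windows | SAEs, AESIs, MAAEs, ARs/SARs | in the sentence; reach unclear |

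If the condition governs the whole list, the uncovered cell is non-serious AESIs and MAAEs in the long-term windows among participants who do not withdraw. Serious AESIs and MAAEs are counted in 17.1.2, but only as SAEs.

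**2. How the sentence can be read**

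- Narrow reading: supported by the section heading, the eCRF flag and the sentence just before it in 17.1.1, whose similar list must be withdrawal-limited to make sense there. An unqualified SAE row would also duplicate 17.1.2.
- Wide reading (the condition attaches only to ARs/SARs): supported by the protocol's placement in 9.4.1, by the word any before SAE, and by the fact that the preceding sentence already tabulates withdrawal events without a time limit.

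Neither reading can be excluded.

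**3. Against the endpoint**

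The modifiers in SAP 3.3 are also loosely attached. On any parse, however, withdrawal is one alternative of an and/or. A MAAE by definition involves a health care visit, so every MAAE meets the consultation alternative. A withdrawal-only table does not estimate that endpoint.

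**4. Days affected, nominal schedule**

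- Inside the 28-day windows: Days 1-57 (57 days) and Days 169-197 (29 days); 57 + 29 = 86.
- Outside: 365 − 86 = 279; 279/365 = 76.4%.
- Check: Days 58-168 (111) + Days 198-365 (168) = 279.

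**5. Illustration with assumed rates**

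The documents give no event or withdrawal rates. Let p be the assumed proportion of the 90 planned participants with a long-term AESI or MAAE, and s the assumed share of those whose event leads to withdrawal. The expected number with events is 90p. The expected number in a withdrawal-only table is 90ps, and the chance that it is empty is (1 − ps)^90.

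| p | s | With events | In withdrawal-only table | Chance table is empty |
|---|---|---|---|---|
| 0.05 | 0.02 | 4.5 | 0.09 | 0.914 |
| 0.10 | 0.05 | 9.0 | 0.45 | 0.637 |
| 0.10 | 0.10 | 9.0 | 0.90 | 0.405 |
| 0.30 | 0.10 | 27.0 | 2.70 | 0.064 |

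At s = 0 the table is always empty.

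**6. Window mismatch**

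The objective in SAP 2.3 and the sentence in 17.1.1 include Day 57-168. The second bullet of SAP 3.3 starts at Day 197. The first bullet, for SAEs, covers both windows.

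**The case against.** The strongest reply is that the sentence was meant widely. The protocol places it under no withdrawal heading, SAP 4.3 declares no change, and it lines up with the two long-term endpoint bullets. The table templates mentioned in SAP Section 9 are not part of the text and could already hold rows for any AESI and any MAAE. This stands as far as it goes: the text is ambiguous, not plainly withdrawal-limited. It does not remove the point, because an analysis plan should not leave the content of a secondary endpoint table to the reader's parsing, and the SAP's own placement pushes toward the narrow reading.

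A reader might infer more than the documents support.

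- **That long-term AESIs and MAAEs would be lost.** They would not. They are collected, protocol 9.4 promises individual listings, and serious cases enter the 17.1.2 table.
- **That MAAEs, AESIs and SAEs are the only events collected throughout these windows.** Under protocol 8.3.1 all AEs are collected on Day 57 and on Days 162-168, which fall inside the first window.
- **That a nearly empty table would by itself give false reassurance.** A table correctly labelled as withdrawals does not claim to count other events. The harm is the absence of the other table.

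**Conclusion.** The point holds as an ambiguity with a definite consequence on one of its two readings. Read as placed in 17.1.1, non-serious long-term AESIs and MAAEs in continuing participants would have no by-group table, and the second secondary safety endpoint would not be estimated. The periods concerned make up 279 of 365 nominal days. No sample size, error rate or data collection is affected. The participant counts in the illustration rest on assumed rates and on the narrow reading. What does not depend on the exact rates is that a withdrawal-only table omits most of these events whenever few of them cause withdrawal. The difference in windows between SAP 3.3 and SAP 2.3 is a separate, smaller inconsistency that holds on either reading.

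**What to change.** 1. Move the long-term sentence out of 17.1.1 into its own subsection.
2. For each window and each treatment group, specify separate rows for any SAE, any AESI and any MAAE, with no withdrawal condition.
3. Give separate rows for events, including ARs/SARs, that lead to withdrawal.
4. If a general AR/SAR row is wanted, limit it to events that are also MAAEs, AESIs or SAEs. Other non-serious ARs are not collected on Days 58-161 or 198-365, so an unrestricted row would be incomplete by design.
5. Reconcile the second bullet of SAP 3.3 with SAP 2.3 and the analysis sentence on whether Day 57-168 is included. Check this against the protocol's own endpoint table, whose secondary safety row is incomplete in the available text.
6. Confirm that the table templates match.

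The cost is SAP wording and table shells. The rows in items 2 to 4 use data already collected.
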